3.5.2 Secondary outcomes

- Strengths and difficulties questionnaire
 - o The 25 item Strengths and Difficulties Questionnaire (SDQ) measures behavioral and emotional function. These 25 items are divided into 5 subscales: emotional symptoms, conduct problems, hyperactivity/inattention, peer relationship

problems, and prosocial behavior.

The Strengths and Difficulties Questionnaire is scored on a 3-point Likert-type scale, with total scores (excluding the prosocial scale) ranging from 0 to 40. Higher scores reflect greater behavioral and emotional difficulties.

o [Time Frame: Baseline, 4th week, 8th week, 12th week]

4. Statistical Analysis Plan (SAP)

Descriptive and inferential statistics will be used. Normally distributed data will be presented by mean and standard deviation (SD) and non-normally distributed data will be presented by median and interquartile range. Categorical data will be presented using percentages. SPSS (version 22.0) will be used for all statistical analyses.

4.1 Primary Outcomes

The primary analyses will find effect i) pilot group guidelines on their mean and standard deviation: (i) Shriners Hospital Upper Extremity Evaluation (SHUEE), (ii) Nine Hole Peg Test. P-values <0.05 will be considered statistically significant.

1*4-Repeated measures analysis of variance (ANOVA) will be performed to test the effectiveness in the intervention between the time intervals (baseline, mid-intervention, post-intervention, and follow-up).

The post–hoc analysis will be conducted to investigate significant effect within the time intervals. Condition on if the sphericity violated (p-value < 0.05), the Greenhouse-Geisser estimated correction will be applied.

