3.1 Research Design Outline

The study aims to perform a pilot study on spastic hemiplegic cerebral palsy children in Aadhuraa Special School and Saveetha Medical College and Hospital.

Formerly titled "Effectiveness of Motion Minder Therapy (MoMT) Among Children with Spastic Hemiplegic Cerebral Palsy: A Pilot Study" involves children with spastic hemiplegic cerebral palsy children by using the Shriners Hospital Upper Extremity Evaluation ¹⁰. The outcome is the total score of the spontaneous functional analysis, dynamic positional analysis, and grasp/release analysis. Total scores of 45 for spontaneous functional analysis, 72 for dynamic positional analysis and 6 for grasp/release. Higher scores mean a better outcome.

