3.5 Assessment & Outcomes Measures

3.5.1 Primary outcomes

- Shriners Hospital Upper Extremity Evaluation (SHUEE)
 - The Shriners Hospital Upper Extremity Evaluation is a video-based tool for the assessment of upper extremity function. The outcome is the total score of the spontaneous functional analysis, dynamic positional analysis, and grasp/release analysis.
 - Total scores of 45 for spontaneous functional analysis, 72 for dynamic positional analysis and 6 for grasp/release. Higher scores mean a better outcome.
 - o [Time Frame: Baseline, 4th week, 8th week, 12th week]

• Nine Hole Peg Test

- Nine Hole Peg Test is used to measure the dexterity. Scores on nine-hole peg test are measured in seconds, indicating time taken to complete task.
- Higher scores indicate worse outcome, as they show slower completion times and reduced dexterity.
- o [Time Frame: Baseline, 4th week, 8th week, 12th week]

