4.3 Missing Data

For children who do not attend the assessment, the mean imputation of the assessment scores from their allocation group will be used.

5. Informed Consent Forms (ICF)

Written consent will be gained from the parents of children with spastic hemiplegic cerebral palsy using the consent forms attached to the application.

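### Sections 4.1 and 4.2 call a one-group test of change between visits the test of effectiveness, but without a comparator a change cannot be attributed to the therapy

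*Combined protocol and SAP*

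**What the plan says.** Section 4.1 states for the two primary outcomes, SHUEE and the Nine Hole Peg Test, that a one-by-four repeated measures ANOVA "will be performed to test the effectiveness in the intervention between the time intervals". The levels of the factor are "baseline, mid-intervention, post-intervention, and follow-up", and p<0.05 counts as significant. A post-hoc "analysis will be conducted to investigate significant effect within the time intervals". Section 4.2 repeats the same plan and the same purpose for the SDQ. Section 3.5 gives the visits as "Time Frame: Baseline, 4th week, 8th week, 12th week".

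Section 3.3 enrols all the children into one pilot study, and Section 4.1 speaks of a pilot group. The visible text describes no control arm, randomisation, crossover, waiting period or second pre-treatment visit.

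The opening of Section 4 plans mean and SD for normally distributed data, and median and interquartile range otherwise. No confidence interval and no SD of change is named. For missed assessments, Section 4.3 says that "the mean imputation of the assessment scores from their allocation group will be used".

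**The concern.** The sentence that defines the primary analysis assigns it a purpose that the design cannot serve. The null hypothesis of the F test is that the four visit means are equal. Rejecting it shows that they differ and leaves the cause open. Children can change over 12 weeks for reasons other than the therapy. For the timed Nine Hole Peg Test, given four times, repeat testing is one plausible rival explanation. With a single measurement before treatment, not even a pre-treatment trend can be estimated.

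No text says how far a significant result may be interpreted, so it could be reported under the plan's own label as effectiveness. Meanwhile, the figures that a pilot can supply for planning a controlled trial (mean change, its CI and the SD of change) are not a planned output. If they were computed after the imputation in 4.3, they would be distorted.

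**Working it through.** **No stated figure to reproduce.** The documents give no sample size, SD, correlation, expected change or missing rate. The core point rests on the text, and every number below is an illustration under assumed inputs.

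**Step 1: label against model.**
- Stated purpose (4.1, 4.2): effectiveness of the intervention.
- Model: one group, one factor (time), four levels, one of them before treatment.
- Hypothesis tested: mean 1 = mean 2 = mean 3 = mean 4.
- Post-hoc comparisons: which visits differ, and in which direction.
- Contrast that would separate therapy from other change: none, because the model has no group term and there is no run-in period.

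**Step 2: the test responds to any real change.** Assume compound symmetry with within-child correlation ρ, n = 20, and a linear non-treatment change of D SD by the last visit, so the means are 0, D/3, 2D/3, D. Power comes from the noncentral F with 3 and 3(n−1) = 57 df and λ = n·Σ(μ − mean μ)²/(1−ρ). For D = 0.3 the sum is 0.3² × 5/9 = 0.05, so at ρ = 0.8 λ = 20 × 0.05/0.2 = 5.

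| D | ρ = 0.5 | ρ = 0.8 | ρ = 0.9 |
|---|---|---|---|
| 0.2 SD | 10% | 20% | 37% |
| 0.3 SD | 18% | 41% | 73% |

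These are powers to detect a real change that the therapy did not cause. They are not type I error rates. They illustrate the logic of Step 1 and add no weight to it.

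**Step 3: what the imputation does to the repaired output.** Assume n = 20 and no true change, with 4 children (20%) missing week 12 at random and given the mean of the other 16. Scores have SD 1. An observed pair has change variance 2(1−ρ). An imputed child has a constant last score, so the change variance is about 1. Approximately, the SD of change = √[0.8 × 2(1−ρ) + 0.2]:
- ρ = 0.5: √(0.80 + 0.20) = 1.00; complete data 1.00; variance ratio 1.0.
- ρ = 0.8: √(0.32 + 0.20) = 0.72; complete data 0.63; ratio 0.52/0.40 = 1.3.
- ρ = 0.9: √(0.16 + 0.20) = 0.60; complete data 0.45; ratio 0.36/0.20 = 1.8.

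A later sample size based on this variance would be larger by the same ratio. Results from 20,000 simulated trials per setting:

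| | ρ = 0.5 | ρ = 0.8 | ρ = 0.9 |
|---|---|---|---|
| SD of change, imputed | 1.00 | 0.73 | 0.61 |
| SD of change, observed pairs | 1.00 | 0.63 | 0.45 |
| 95% CI half-width, imputed (SD) | 0.46 | 0.33 | 0.28 |
| 95% CI half-width, observed pairs (SD) | 0.52 | 0.33 | 0.23 |
| CI coverage, imputed | 92.7% | 92.8% | 93.3% |
| CI coverage, observed pairs | 95.0% | 94.9% | 95.1% |
| ANOVA p<0.05, complete data, uncorrected | 4.8% | 5.1% | 4.9% |
| ANOVA p<0.05, imputed, uncorrected | 7.2% | 7.6% | 7.9% |

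With the plan's own rule (Greenhouse-Geisser only when sphericity is rejected), the imputed false-positive rate is about 7%. Correcting every time would bring it to about 6%. Repeat simulations put coverage after imputation between about 92% and 94%. At ρ = 0.9 the imputed interval is both wider than the one from observed pairs and less reliable, because imputation breaks the pairing.

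**The case against.** The strongest reply is that this is a pilot and says so. One group, four visits and a repeated measures ANOVA form a legitimate pilot design, and the null hypothesis tested stays the same after rewording. The plan states no rule that p<0.05 will be read as proof of effectiveness, so the harm is conditional. All of that stands. It limits the fault to the stated purpose and the absence of any limit on the conclusion, and it does not remove either.

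Several stronger readings are tempting but unsupported:
- **The F test cannot show direction or timing.** This is true of the omnibus test alone, but the planned post-hoc comparisons and visit means supply both.
- **The title proves an effectiveness claim.** Section 3.1 quotes "Effectiveness of Motion Minder Therapy (MoMT) Among Children with Spastic Hemiplegic Cerebral Palsy: A Pilot Study" but introduces it as a former title. The current title is not visible, so this is weak evidence.
- **Practice effects bias every outcome.** Repeat testing is a plausible rival for the timed peg test only. For SHUEE and the SDQ, the limit is the missing comparator.
- **Pegboard work in the sessions confounds the peg test.** It is part of the therapy, so the overlap bears on whether a gain is task-specific.
- **The reference to an allocation group in 4.3 implies a second arm.** Nothing else supports this, and a one-by-four model could not use one.

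It is also fair to say that the imputation is a separate weakness of moderate size. It belongs here only because the repaired output would inherit it.

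**Conclusion.** The point holds in this form: the plan names as a test of effectiveness an analysis that can show change between visits but not its cause, and no visible text limits the conclusion. This applies to every inferential analysis in the SAP, primary and secondary. It rests on the wording and the design, and needs none of the assumed figures. A reader might infer that the ANOVA is invalid or that a one-group pilot is unacceptable. The documents support neither reading.

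The figures on imputation (coverage about 92-94%, false positives about 7%, variance of change up to 1.8 times as large) hold for 20 children, 20% missing at random at week 12, compound symmetry and correlation 0.5 to 0.9. At correlation 0.5 the SD of change is not inflated, although coverage and error rate are still affected.

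**What to change.** 1. In 4.1 and 4.2, replace the stated purpose with estimation of within-child change over time. Add that no effectiveness conclusion will be drawn from the one-group data.
2. Report the change from baseline to week 8 and to week 12 (post-intervention and follow-up, if the visit labels run in order). Give each a 95% CI and the SD of change, or median change with interquartile range if change is skewed, in line with the opening of Section 4. Give the number of observed pairs and the reasons for missing visits.
3. Do not apply the group-mean imputation of 4.3 to these estimates or to the supporting test. Fit the time effect with a mixed model for repeated measures on all observed scores. Alternatively, keep the ANOVA, state that it uses only children with all four visits, and give that number.
4. Separately, reconcile the allocation-group wording in 4.3 with the one-group design. Align the title quoted in 3.1 only if it is still in use.

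The cost is wording in 4.1 to 4.3 (and 3.1 if needed) and one table, with no new visits or data. The downsides are a more modest claim and reliance on assumptions about missing visits: observed pairs need missingness unrelated to change, and the mixed model needs missing at random.

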4.2 Secondary Outcomes

The primary analyses will find effect i) pilot group guidelines on their mean and standard deviation: (i) Strength and Difficulties Questionnaire (SDQ). P-values <0.05 will be considered statistically significant.

1*4-Repeated measures analysis of variance (ANOVA) will be performed to test the effectiveness in the intervention between the time intervals (baseline, mid-intervention, post-intervention, and follow-up).

The post–hoc analysis will be conducted to investigate significant effect within the time intervals. Condition on if the sphericity violated (p-value < 0.05), the Greenhouse-Geisser estimated correction will be applied.

4.3 Missing Data

For children who do not attend the assessment, the mean imputation of the assessment scores from their allocation group will be used.

5. Informed Consent Forms (ICF)

Written consent will be gained from the parents of children with spastic hemiplegic cerebral palsy using the consent forms attached to the application.

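### Filling missed assessments with the group mean ignores the child's own scores, and can create a false time effect and raise the type I error of the repeated measures ANOVA

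*Combined protocol and SAP*

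**What the plan says.** Section 4.3 is the whole missing-data plan. It applies "For children who do not attend the assessment", with no distinction by reason or number of missed visits, and states that "the mean imputation of the assessment scores from their allocation group will be used". It does not say whether the mean is taken at the missed visit or pooled over visits. It refers to an allocation group although the design has only one group. It gives no assumed mechanism, no allowance for imputation uncertainty and no sensitivity analysis.

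The filled data go into the analysis in section 4.1: "1*4-Repeated measures analysis of variance (ANOVA) will be performed to test the effectiveness in the intervention between the time intervals". Each outcome is tested at 0.05, with this provision: "Condition on if the sphericity violated (p-value < 0.05), the Greenhouse-Geisser estimated correction will be applied". Section 4.2 applies the same model and threshold to SDQ. All outcomes are assessed at baseline and weeks 4, 8 and 12 (sections 3.5.1 and 3.5.2).

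**The concern.** The ANOVA works on each child's change over time. A group mean in place of a missed score gives that child a change that never occurred.

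- **Bias.** If poorer-functioning children are absent, their low SHUEE scores are replaced by a higher mean and the group appears to improve. The Nine Hole Peg Test errs the same way, because on that test "Higher scores indicate worse outcome, as they show slower completion times and reduced dexterity": long times are replaced by a shorter mean. If better-functioning children are absent, the result is a false deterioration. The documents give no reason to expect either direction.
- **Type I error.** Imputed values are analysed as observed. They add error degrees of freedom but no information. With a visit-specific mean, the error can therefore rise even when visits are missed at random.

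Section 4.1 uses this test to judge effectiveness, and there is no control group in which a shift caused by absence could cancel.

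**Working it through.** **Inputs from the documents:** one group, four visits, alpha 0.05, Greenhouse-Geisser only if the sphericity test has p < 0.05, group-mean imputation. **Assumed, because the documents are silent:** sample size n, missing rate, mechanism, within-child correlation, and visit-specific or pooled mean. The plan states no figure to reproduce other than the nominal 5%.

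**1. A shifted mean when nobody changes.** Suppose five children score 30, 40, 50, 60 and 70 on the 72-point SHUEE part at every visit, and the child with 30 misses weeks 8 and 12.

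- True mean at every visit: 250/5 = 50.
- Visit-specific rule: imputed value (40+50+60+70)/4 = 55; week-8 mean (220+55)/5 = 55.
- Pooled rule: the 18 observed scores sum to 2×30 + 4×220 = 940; imputed value 940/18 = 52.2; week-8 mean (220+52.2)/5 = 54.4.

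This example shows bias only. Under the visit-specific rule the planned ANOVA gives F(3,12) = 1.00, p = 0.43.

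**2. Expected bias in a large sample.** If the lowest fraction q on baseline is absent and the correlation with the later visit is ρ, the later mean shifts by ρ·φ(z_q)/(1−q) SD. With q = 0.20, z = −0.842 and φ = 0.280, this is 0.8 × 0.280/0.80 = 0.28 SD. If absence is ranked on baseline plus independent noise of equal variance (correlation 0.71 with baseline), it is 0.71 × 0.28 = 0.20 SD. The simulated values at n = 20 were 0.27 and 0.19 SD.

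**3. Type I error of the planned test.** The settings were no true change, equal correlation 0.8, visit-specific mean, absence at weeks 8 and 12, and 20,000 replicates. The simulation standard error near 5% is √(0.05×0.95/20,000) = 0.15 points. With complete data at n = 20 the error was 4.7%.

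| n | Missing | Lowest baseline absent | Moderate dependence | Random |
|---|---|---|---|---|
| 10 | 10% | 4.3% | 5.3% | 6.4% |
| 10 | 20% | 9.3% | 8.5% | 8.3% |
| 20 | 5% | 4.3% | 4.9% | 5.5% |
| 20 | 10% | 7.6% | 7.0% | 6.5% |
| 20 | 20% | 23.8% | 16.8% | 8.8% |
| 30 | 10% | 12.4% | 10.1% | 6.7% |
| 30 | 20% | 43.6% | 27.6% | 9.3% |

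Variations at n = 20 with 20% missing:

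- Pooled mean: 19.3 / 11.7 / 4.9%.
- AR(1), 0.8 between adjacent visits: 11.1 / 10.2 / 8.4%.
- Highest-baseline children absent: false change −0.26 SD, error 23.2%.

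Further runs (10,000 replicates, visit-specific mean, n = 10 to 30, correlation 0.5 to 0.9, 20% missing) gave 6.2 to 9.8% for random loss of the last two visits and 10.9 to 13.5% for random intermittent absence. Baseline-dependent loss gave 6.7 to 56.5%, with a false gain of 0.14 to 0.27 SD.

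**4. Does the remedy work?** An unstructured REML model with Kenward-Roger tests matched Hotelling's T-squared exactly on complete data. With 20% missing, n = 10 to 30, correlation 0.8, both covariance patterns and all three mechanisms (3,000 replicates per setting), bias was within 0.01 SD and error 4.4 to 7.7%. All 72,000 fits converged. A second coding in fewer settings gave about 5 to 6% at n = 20 to 30 and 6 to 9% at n = 10. Alternatives:

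- Unstructured with Satterthwaite: 6.7 to 15.6%.
- Random intercept: 6.7 to 6.8% on complete AR(1) data.
- Complete-case ANOVA, lowest-baseline 20% absent: 5.8 to 7.7% (equal correlation) and 8.3 to 13.4% (AR(1)), with a false change of −0.06 to −0.12 SD.

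**The case against.** **Size.** The large figures need a fifth of the children absent at both late visits, selected by baseline. With one absent child (n = 10 at 10%, n = 20 at 5%) the error is 4.3 to 6.4%. In a single-group pilot, maturation and practice already confound the time effect. This stands as a limit on size. It does not rescue the rule: random absence at 20% still gives 8.3 to 9.3% with the visit-specific mean, and bias from selective absence comes on top of other confounding.

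**Detectability.** Absent children are known, so comparing their baselines with those of attenders would reveal a baseline-related shift. That is true, but the plan includes no such comparison, and the planned test cannot make the distinction.

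**Pooled mean.** Under random absence and equal correlation it kept the error at 3.8 to 5.2%. It also shrinks a real effect. In one setting (n = 20, correlation 0.8, 20% missing) a true gain of 0.50 SD was estimated as 0.46, and power fell from 93% to 76%. The pooled reading is therefore no escape.

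**Remedy.** A random-intercept REML model gave 4.5 to 5.9% under equal correlation with 20% missing, so the case against it rests on unequal correlations, where the excess seen was modest. At n = 10 the unstructured model's error is not clearly better than that of the planned ANOVA under random absence. The gain there is mainly removal of bias. The fallback covariance was not tested. These points bear on detail, not on whether to drop group-mean imputation.

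**Conclusion.** The concern holds. Section 4.3 puts a value unrelated to the child into a within-child analysis and treats it as observed, for every outcome tested. When absence depends on function, the time effect is biased in a direction set by who is absent. With a visit-specific mean, the type I error can also rise under random absence. At n = 20, 20% missing and equal correlation 0.8, the error is 8.8 to 23.8% and the false gain 0.00 to 0.27 SD, depending on mechanism. These figures rest on assumed inputs. With very few absences the harm is small, and with none the rule is never used. The reference to an allocation group is a minor wording slip.

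**What to change.** Delete the mean-imputation rule and the reference to an allocation group. In sections 4.1 to 4.3, specify for SHUEE, the Nine Hole Peg Test and SDQ:

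- A REML linear mixed model on all observed assessments, without imputation, with visit as a four-level fixed effect, unstructured covariance within child and Kenward-Roger tests. Take the post-hoc visit comparisons as contrasts from the same model.
- One named fallback for non-convergence: heterogeneous first-order autoregressive, which suits visits spaced 4 weeks apart. A plain random intercept would drop the sphericity protection that section 4.1 provides.
- Complete-case repeated measures ANOVA with Greenhouse-Geisser as a sensitivity analysis only.
- Numbers missing and reasons by visit, with a statement that the model assumes absence depends only on observed scores.

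Section 4 states that "SPSS (version 22.0) will be used for all statistical analyses". If that version does not offer Kenward-Roger, name software that does. Satterthwaite is not an adequate substitute here.

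Cost: rewritten analysis text, somewhat more complex syntax, possibly other software, and a risk of non-convergence in a very small sample. No extra data or children are needed.
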